**Table 4: Primary Analysis Visit Windows**

Scheduled Visit	Target Study Day	Analysis Window (Study Day Range)
Week 2	14	2 to 21
Week 4	28	22 to 36
Week 6	42	37 to 53
Week 9	63	54 to 74
Week 12	84	75 to 98
Week 16	112	99 to 126
Week 20	140	127 to 154
Week 24	168	155 to (first dose date in OL period)
Month 7	196	(First dose date in OL +1) to 210
Month 8	224	211 to 238
Month 9	252	239 to 266
Month 10	280	267 to 308
Month 12	336	309 to (first dose date in OL/DB period)

**Table 5: Primary Analysis Visit Windows for Subjects Who Discontinue Study Drug Prior to Week 24 or prior to Month 12**

Scheduled Visit	Target Study Day	Analysis Window (Study Day Range)
Week 2	14	2 to 21
Week 4	28	22 to 36
Week 6	42	37 to 53
Week 9	63	54 to 74
Week 12	84	75 to 98
Week 16	112	99 to 126
Week 20	140	127 to 154
Week 24	168	155 to 182

Scheduled Visit	Target Study Day	Analysis Window (Study Day Range)
Month 7	196	183 to 210
Month 8	224	211 to 238
Month 9	252	239 to 266
Month 10	280	267 to 308
Month 12	336	309 to 350
DB Safety Follow-up a*	Day of last dose of study drug in DB period + 28 Days	Study day of last dose of study drug in DB period + 14 days to day of last dose of study drug in DB period + 42 days
OL Safety Follow-up b*	Day of last dose of study drug in OL period + 28 Days	Study day of last dose of study drug in OL period + 14 days to day of last dose of study drug in OL period + 42 days

\*Note that only safety labs, vital signs, ECG, and BPRS assessments will be mapped to the “DB Safety Follow-up” and “OL Safety Follow-up” visits. Visits that qualify for DB safety follow-up or OL safety follow-up will take precedent over any other visit window that the assessment qualifies for.

aSubjects who discontinue study and study drug in the DB period and have a visit in the study day range specified will have their safety data mapped to the “DB Safety Follow-up.”

bSubjects who discontinue study and study drug in the OL period and have a visit in the study day range specified will have their safety data mapped to the “OL Safety Follow-up.”

Bone mineral density and testicular ultrasound analysis visit windows are presented in [Table 6](#). These assessments have a wider visit window (including a qualifying baseline assessment) as these parameters are not expected to change to a degree that could be clinically detected over this time frame.

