^c Within 1 week after the visits at Months 7, 8, 9, 13 (only for re-randomized subjects), 14 (only for re-randomized subjects), and 16 (only for re-randomized subjects), if a glucocorticoid dose reduction occurred, the study site will call the subject for a safety follow-up. If needed, the subject may come in for an unscheduled visit for a safety follow-up (eg, vital signs, laboratory assessments).

^d Only for re-randomized subjects.

^e For subjects who discontinue the study prior to Month 18, assessments will be performed at the ET visit and at the follow-up visit (a follow-up visit is not required if the last dose of study drug was at least 28 days prior to the ET visit). Subjects who complete the Month 18 visit and elect to not enter the OLE will undergo a follow-up visit approximately 28 days after last dose of study drug.

^f Includes measurement of waist circumference.

^g After vital signs are obtained, measure blood pressure (single measurement) and heart rate again after the subject has been standing (from a seated position) for approximately 2 minutes. Compare the standing blood pressure vs the average of the 3 sitting blood pressures for evaluation of orthostasis criteria. Repeat once if abnormal (systolic blood pressure decrease >20 mm Hg, or diastolic blood pressure decrease >10 mm Hg).

^h Measure blood pressure 3 times, in up to 1-minute intervals, after the subject has been sitting quietly for at least 5 minutes. Height and weight will be measured with subjects not wearing shoes; weight will be measured with subjects not wearing outerwear (eg, jackets or coats).

ⁱ For all females of childbearing potential.

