9.6.3. Vital Sign Measurements Including Height and Weight

Vital sign measurements, including systolic and diastolic blood pressure, pulse rate, respiratory rate, and body temperature (oral, axillary, tympanic or temporal artery), as well as body weight will be measured. Blood pressure and pulse rate will be measured 3 times, in up to 1-minute intervals, using a Sponsor-provided calibrated automatic blood pressure cuff (with the exception of at-home visits) after the subject has been sitting quietly for at least 5 minutes. Height and weight will be measured with subjects not wearing shoes; weight will be measured with subjects not wearing outerwear (eg, jackets or coats).

Vital sign measurements including weight will be obtained before any scheduled blood sample collection at screening, Day 1 (baseline), Weeks 4, 6, 9, 12, 16, 20, 24, and Months 7, 8, 9, 10, 12, 13 (for subjects re-randomized at Month 12), 14, 16, 18, 21, 24, and every 6 months thereafter. Vital signs will also be obtained at early termination and at the Follow-Up Visit. Height will be measured at screening only.

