The primary endpoint of percent change from baseline in glucocorticoid daily dose at Week 24 is based on the glucocorticoid concomitant medications eCRF. The method of collecting concomitant medication data involves entering a start date and stop date for each medication, unless it is ongoing, in which case the “Ongoing?” field is marked as “yes.” This differs from assessments that are collected discretely at visits. Additionally, the androstenedione values collected at the Week 24 visit are a critical component to the assessment of this endpoint as subjects who do not maintain androstenedione control will have their percent change from baseline value in glucocorticoid total daily dose set to 0. For the purposes of determining the glucocorticoid total daily dose from the eCRF at Week 24, the Week 24 visit date at which the androstenedione values were collected (based on the analysis visit mapping described below) will be used to determine the glucocorticoid dose (as of the same date) to be used for the primary endpoint. If a subject has a Week 24 visit performed based on the analysis visit window but androstenedione was not collected at this visit (ie, missed hormone labs), then the analysis visit date from the collection of the safety labs will be used instead for determining the Week 24 glucocorticoid total daily dose. If both hormone and safety labs were missed at the visit, then the vital signs assessment and its respective Week 24 analysis visit date will be used for determining the glucocorticoid total daily dose. The same methodology described above will be used to determine the glucocorticoid total daily dose from the eCRF at each of the other intermediate visits.

[Table 4](#) includes the analysis visit windows for all assessments, with the exception of those assessments that have a broader window due to more infrequent assessments (eg, every 6 months). These more-infrequent assessments include measurements obtained via DXA (bone mineral density and body composition), testicular ultrasound measurements, HbA1c, glucose tolerance test, insulin, bone markers, and lipid panel. These assessments will use the analysis visit windows defined in [Table 6](#), [Table 7](#), and [Table 8](#), as applicable. [Table 5](#) includes the analysis visit windows for subjects who discontinue from study drug prior to OL period or OL/DB period and therefore do not have a first dose date in the OL period or OL/DB period.

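### Two unqualified window rules in SAP Table 5 can misplace Week 24 efficacy records in a small number of subjects who stop study drug

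*SAP*

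**What the plan says.** **General windows.** SAP Table 4 runs Week 24 from Day 155 to the date of the first open-label dose. Month 7 starts the next day and ends on Day 210.

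**Stoppers' windows.** Table 5 is titled "Primary Analysis Visit Windows for Subjects Who Discontinue Study Drug Prior to Week 24 or prior to Month 12". Section 6.7 describes its users as "subjects who discontinue from study drug prior to OL period or OL/DB period and therefore do not have a first dose date" in those periods. Its rows are fixed: Week 24 is Days 155 to 182, Month 7 is Days 183 to 210 and Month 12 is Days 309 to 350. It also has double-blind and open-label safety follow-up rows.

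**Safety follow-up.** The double-blind follow-up row opens at "Study day of last dose of study drug in DB period + 14 days" and closes at 42 days. Under the table notes it takes only safety labs, vital signs, ECG and BPRS, and only from subjects who leave both study and drug in that period. The precedence rule reads "Visits that qualify for DB safety follow-up or OL safety follow-up will take precedent over any other visit window that the assessment qualifies for".

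**Selection.** Section 6.7 remaps unscheduled, repeat and early termination visits as well as scheduled ones. Within a window the record closest to target is used, and a tie goes to the earlier record. The Week 24 glucocorticoid dose is read on the date of the Week 24 androstenedione sample. If that sample is absent, the date comes from the safety labs, and failing those from the vital signs.

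**Endpoints touched.** Blood pressure at Week 24 is a secondary endpoint on observed cases (SAP 9.5, 9.5.2). Percent change in weight at Week 24 is a key secondary endpoint with multiple imputation (SAP 9.4.4). Protocol 9.6.3 groups weight with vital signs: "Vital sign measurements including weight will be obtained before any scheduled blood sample collection".

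**The concern.** Blood pressure is one record with two uses, safety and efficacy. The precedence rule removes it from Week 24 without saying that this applies to safety tables only. An observed Week 24 value can then be dropped (blood pressure) or replaced by imputation (weight, if it moves too), while a hormone sample from the same visit still counts as Week 24.

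For open-label stoppers, the stated reason for Table 5 is a missing first dose date. They lack the date for the Month 12 to 18 period but have the open-label one. Applying the fixed Week 24 row to them removes the boundary between double-blind and open-label data. A sample taken on crinecerfont could stand as the Week 24 value of a subject randomized to placebo. Because the glucocorticoid dose date follows the androstenedione date, this route reaches the primary endpoint. In both cases the placement of a Week 24 record turns on what the subject does afterwards.

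**Working it through.** **Reproducing the Table 5 rows.** Targets are Day 140 (Week 20), 168 (Week 24) and 196 (Month 7). The midpoints are (140 + 168)/2 = 154 and (168 + 196)/2 = 182. With a tie given to the earlier visit, Week 24 is Days 155 to 182 and Month 7 starts on Day 183, as printed.

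**Part 1: subjects who leave drug and study.** Let L be the day of the last double-blind dose.

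- The follow-up window is L + 14 to L + 42. It overlaps Days 155 to 182 when L + 42 ≥ 155 and L + 14 ≤ 182, so L is Day 113 to 168. This is the outer limit.
- Protocol 9.7.6.1 puts the final visit at 28 days after the last dose, +7 days for subjects not in the extension. A visit at L + 28 to L + 35 can land in Week 24 when L + 35 ≥ 155 and L + 28 ≤ 182, so L is Day 120 to 154. At exactly 28 days, L is Day 127 to 154.
- An early termination record before L + 14 is not moved. It can fill Week 24 only if it falls on Day 155 or later, which needs L + 13 ≥ 155, so L ≥ 142. For L up to 141 it cannot.

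Example: last dose Day 130, early termination visit Day 137, final visit Day 130 + 28 = 158. Day 137 lies in the Week 20 window (127 to 154). Day 158 lies in Week 24, but also in the follow-up window (Days 144 to 172), which wins. Hormones from Day 158 stay at Week 24 and blood pressure leaves it. A subject may also have just one close-out visit, since "a follow-up visit is not required if the last dose of study drug was at least 28 days prior to the ET visit".

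**Part 2: open-label stoppers.** Let F be the day of the Week 24 visit. Open-label drug starts that evening (protocol Section 7), so F is also the first open-label dose day. The visit window of ±5 days (protocol 9.7.2.3.3) gives F = 163 to 173. Under Table 5, a later record on day d replaces the visit if d ≤ 182 and |d − 168| < |F − 168|.

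| F | Distance from Day 168 | Days that displace the visit |
|---|---|---|
| 163 | 5 | 164 to 172 (173 ties, earlier kept) |
| 165 | 3 | 166 to 170 |
| 168 | 0 | none |
| 173 | 5 | none |

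Only visits before Day 168 are exposed to displacement. The next scheduled sample is Month 7, at Day 196 − 5 = 191 at the earliest, so the displacing record must be unscheduled, a repeat or an early termination sample.

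A Week 24 visit on Day 184 is Week 24 under Table 4 and Month 7 under Table 5. That is 184 − 173 = 11 days beyond the visit window. It would need the sick-day provision, which overrides visit windows (protocol 9.3.1), or a deviation.

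**Size of Part 1.** The documents give no dropout rate. Assume that 5% to 15% of 165 subjects leave (8.25 to 24.75) and that last doses are uniform over Days 1 to 168. Those with L on Days 120 to 154 (35 days) number 8.25 × 35/168 = 1.7 to 24.75 × 35/168 = 5.2. These are upper figures: some will have no final visit, one outside the window, or another in-window record. Part 2 needs several events in one subject and cannot be sized from the documents.

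**The case against.** **The follow-up rule is meant for safety data.** The footnote to the double-blind row speaks of safety data, and SAP Section 11 introduces the follow-up summary for by-visit safety tables. That is probably the intent. But the precedence sentence is unqualified, and blood pressure is a vital sign whichever table it feeds.

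**Weight may not be a vital sign here.** Protocol 9.6.3 groups the two. The protocol synopsis lists weight separately, and SAP 11.4 does not name it. This stands: the effect on a key secondary endpoint is conditional on how weight is handled.

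**Table 5 should be read respectively**, replacing only the date a subject lacks. Tables 6 to 8 anchor Week 24 to the first open-label dose, and SAP 6.3.2 requires open-label baseline values to precede that dose. This again shows likely intent. The Table 5 title and its open-label follow-up row still bring open-label stoppers under the table, and nothing preserves Table 4's cut for them.

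**Stronger readings do not hold.** A reader might infer that the sponsor plans to use on-crinecerfont values as placebo Week 24 data; the documents state no such intention. A reader might count every leaver with a last dose on Days 113 to 168 as affected, but that range includes off-schedule visits and subjects whose earlier record still fills Week 24. Subjects who stop drug and stay in the study are not moved to double-blind follow-up at all. Hormones are not moved, so Part 1 reaches the primary endpoint only through the dose-date fallback when the hormone sample was missed. Nor does the Month 12 lock re-open the confirmatory test, which belongs to the Week 24 final analysis (SAP 5.2). Part 2 matters there only for subjects who have already stopped open-label drug by that lock.

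**Conclusion.** Both defects follow from the text as written, and both are drafting errors. The plan can lose an observed Week 24 blood pressure (and weight, if it travels with vital signs) for subjects who leave drug and study, mainly with last doses on about Days 120 to 154 and no other in-window record. For open-label stoppers it can let a post-switch sample displace a Week 24 visit held before Day 168, or push a Week 24 visit after Day 182 into Month 7.

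The expected numerical effect is small: under the stated dropout assumptions, at most about 2 to 5 subjects for Part 1, and probably fewer for Part 2. Tipping-point and complete-case analyses exist for the primary endpoint and weight, but they vary or omit missing values and would not restore a misfiled record. The point should be corrected because it lets events after the endpoint decide which Week 24 value is used. It is not a threat to the trial's conclusions.

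**What to change.** Before database lock, add to SAP 6.7:

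1. The safety follow-up precedence applies only to by-visit safety displays. Blood pressure and weight used for efficacy keep their Week 24 mapping.
2. Every subject with a first open-label dose date uses Table 4's boundary between Week 24 and Month 7, cut at that date. Table 5's Week 24 end (Day 182) and Month 7 start (Day 183) apply only where that date does not exist. Its Month 12 end (Day 350) applies only where the first dose date for the Month 12 to 18 period does not exist.

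The cost is two short statements and a programming flag. A blood pressure record may then appear both in the safety follow-up table and in the Week 24 efficacy analysis, which a table footnote can explain.

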**Table 6: Analysis Visit Windows for Bone Mineral Density and Testicular Ultrasound**

Scheduled Visit	Target Study Day	Analysis Window (Study Day Range)
Week 24	168	84 to (first dose date in OL period + 28)
Month 12	336	252 to (first dose date in OL/DB period + 28)

Analysis visit windows for body composition assessments are presented in [Table 7](#).

**Table 7: Analysis Visit Windows for Body Composition**

Scheduled Visit	Target Study Day	Analysis Window (Study Day Range)
Week 24	168	84 to (first dose date in OL period + 14)
Month 12	336	252 to (first dose date in OL/DB period + 14)

Analysis visit windows for the glucose tolerance test, HbA1c, bone markers, and lipid panel assessments are presented in [Table 8](#).

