^j Collect blood sample for hormone measurements (adrenocorticotrophic hormone [ACTH], 17-hydroxyprogesterone [17-OHP], cortisol, androstenedione, testosterone, luteinizing hormone [LH], follicle stimulating hormone [FSH], progesterone, plasma renin activity [PRA; measured upright], and sex hormone binding globulin [only for the second blood sample collected at Months 12, 13, and 18]) in the morning approximately 2 to 3 hours after the morning glucocorticoid dose. At Month 12, Month 13 (only for re-randomized subjects), and Month 18/early termination, collect additional blood sample prior to morning glucocorticoid dose. The second blood sample should be collected prior to 1100 hours. Subjects not on a morning glucocorticoid should still have 2 morning blood samples taken (with the glucose tolerance test and/or before and after the morning study drug dose). The last dose of glucocorticoid taken prior to the first blood sample should be documented.

^k Urine sample should be collected by the subject at home starting at midnight the night before the visit until the first morning void after awakening for the day using a container provided to the subject and brought to the study center.

^l Collect blood sample after subject fasting at least 8 hours for glucose, insulin, total cholesterol, low-density lipoprotein, high-density lipoprotein, triglyceride, and glycated hemoglobin (HbA1c).

^m Collect blood sample for osteocalcin, bone-specific alkaline phosphatase, and C-terminal telopeptide (CTx) and collect urine sample (fasting, after first morning void) for N-terminal telopeptide (NTx).

ⁿ After an overnight fast (minimum of 8 hours), collect blood samples prior to (within 30 minutes) and approximately 2 hours after 75-gram glucose load (only in subjects without diabetes mellitus).

^o For males only. Testicular ultrasound is not required during an early termination visit if the subject had a testicular ultrasound within 3 months prior.

^p Not required during an early termination visit if the subject had a DXA within 3 months prior.

^q For female subjects only. Menstrual questionnaire only for females of childbearing potential not on hormonal or intrauterine device contraceptives.

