The second key secondary endpoint is the achievement of a reduction in glucocorticoid daily dose to physiologic levels ($\leq 11 \text{ mg/m}^2/\text{day}$ hydrocortisone equivalents adjusted for BSA) at Week 24, while Week 24 androstenedione is adequately controlled at $\leq 120\%$ of baseline or $\leq \text{ULN}$ for age and sex. Androstenedione levels used to assess adequate control is as described for the primary endpoint above. The primary analysis of this endpoint will be performed using a Cochran-Mantel-Haenszel (CMH) test. The CMH test will compare treatment groups and will include the stratification factors used in the randomization. Subjects whose androstenedione levels at Week 24 are not controlled will be considered non-responders. Subjects who are missing their glucocorticoid dose or all androstenedione data at Week 24 will have their data imputed through a multiple imputation procedure. Missing data will be imputed for subjects in the crinecerfont treatment group using retrieved data (ie, observed data from subjects who discontinued study drug) in the crinecerfont treatment group, provided there is sufficient retrieved data. Otherwise, missing data will be imputed using observed data from subjects in the placebo treatment group. For subjects in the placebo treatment group, missing data will be imputed using observed data from subjects in the placebo treatment group. This analysis will be performed using the FAS.

Additional key secondary endpoints are the changes from baseline in HOMA-IR, weight, and fat mass at Week 24, which will be analyzed using an ANCOVA model. The model will include treatment group, corresponding baseline values, and stratification factors used in the randomization. Subjects who are missing data at Week 24 will have their data imputed through a multiple imputation procedure using the retrieved data method as described for the first key secondary endpoints above. This analysis will be performed using the FAS.

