## 6.7. Study Day

For each subject, study day is calculated relative to Day 1, where Day 1 is defined as the date of first dose of study drug. If the date of interest occurs on or after Day 1, then the study day will be calculated as: date of interest – date of Day 1 + 1. If the date of interest occurs prior to Day 1, then the study day will be calculated as: date of interest – date of Day 1. For subjects who are randomized but never dosed, Day 1 will be defined as the subject's randomization date.

The nominal visit number for each visit, including scheduled, unscheduled, repeat, and early termination/end of study visits, will be re-mapped to an analysis visit according to [Table 4](#), [Table 5](#), [Table 6](#), [Table 7](#), [Table 8](#). If multiple measurements occur within the same visit window after mapping, the measurement that is closest to the target study day will be used for the summary tables where one observation per visit is needed, unless otherwise specified. Where there are ties between the earlier and later observation within the visit window, the earlier observation will be used. For the purpose of this study, months are defined as 4-week intervals.

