**Table 8: Analysis Visit Windows for Glucose Tolerance Test, HbA1c, Bone Markers, and Lipid Panel**

Scheduled Visit	Target Study Day	Analysis Window (Study Day Range)
Week 24	168	84 to (first dose date in OL period)
Month 12	336	252 to (first dose date in OL/DB period)

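### An early-termination DXA from Day 84 onward counts as the observed Week 24 percent fat mass and bypasses the planned imputation

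*SAP*

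**What the plan says.** - **Mapping rule.** SAP 6.7 says that visits, "including scheduled, unscheduled, repeat, and early termination/end of study visits, will be re-mapped to an analysis visit". If several values share a window, the one closest to the target day is used.
- **Wide windows.** SAP 6.7 sends infrequent assessments to Tables 6 to 8: DXA measurements, testicular ultrasound, "HbA1c, glucose tolerance test, insulin, bone markers, and lipid panel. These assessments will use the analysis visit windows defined in" those tables. Table 7 (body composition) opens Week 24 at Day 84 and closes 14 days after the first open-label dose: "84 to (first dose date in OL period + 14"). Table 8 reads "84 to (first dose date in OL period").
- **Narrow windows.** Table 4, which covers weight, reads "155 to (first dose date in OL period") for Week 24. Table 5, for subjects who stop drug before Week 24 or Month 12, gives 155 to 182.
- **Exit assessments.** Protocol 9.10.2 asks all withdrawing subjects for the early-termination assessments. Protocol 9.7.4.5 lists a fasting metabolic panel and a DXA among them. On the DXA, Protocol Table 2 adds: "Not required during an early termination visit if the subject had a DXA within 3 months prior".
- **Missing data.** For HOMA-IR, weight and fat mass, Protocol 13.6.1.3 states: "Subjects who are missing data at Week 24 will have their data imputed through a multiple imputation procedure". SAP 9.4.5 and 16.2 apply this only where the Week 24 value is absent.
- **Stated reason.** The text before SAP Table 6 justifies wider windows "as these parameters are not expected to change to a degree that could be clinically detected over this time frame". It says this of bone mineral density and testicular ultrasound only.

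**The concern.** Percent total fat mass belongs to the last Holm family of key secondary endpoints (SAP 9.1). Its Week 24 window admits scans taken as much as 12 weeks early. Nearly all such scans would be exit scans, because no DXA is scheduled between Day 1 and Week 24. For a subject who leaves the study, the exit value then stands in for Week 24. In effect this is a carry-forward, and it replaces the imputation from retrieved dropouts or placebo that both documents describe.

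The planned sensitivity analyses would not reveal it. The tipping-point analysis in SAP 16.5 shifts only values that were missing to begin with, and the complete-case analysis in SAP 9.4.5 keeps whatever counts as observed. The early value passes unchanged through both.

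**Working it through.** **1. Reproducing the window limits.** Week 12 is 12 × 7 = Day 84 and Week 24 is 24 × 7 = Day 168. The midpoint 168/2 = 84 is the Table 7 lower limit, and (168 + 336)/2 = 252 is its Month 12 lower limit. The narrow cut is (140 + 168)/2 = 154. Day 84 therefore looks like a deliberate midpoint and not a typing error.

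**2. How early a value may be.** Table 7 allows 168 − 84 = 84 days before target. Tables 4 and 5 allow 168 − 155 = 13 days, so the ratio is 84/13 = 6.5. The additional days are 154 − 84 + 1 = 71, covering most of the Week 12 window and all of the Week 16 and Week 20 windows.

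**3. When an exit DXA is due.** The study counts a month as 4 weeks, so 3 months is 3 × 28 = 84 days. With the last DXA at about Day 1, an exit DXA becomes due at about the day the Week 24 window opens.

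**4. One subject traced.** Take a crinecerfont subject who stops drug and leaves the study with an exit visit on Day 90.

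| Item from the Day 90 visit | Window applied | Treatment at Week 24 |
|---|---|---|
| Weight | Table 5: Week 12 is 75 to 98, Week 24 is 155 to 182 | Missing, imputed under SAP 16.2 |
| Percent total fat mass | Table 7: Week 24 from Day 84 | Observed, not imputed |
| Insulin | Named as wide-window in SAP 6.7, not in the Table 8 title | Unclear |
| Fasting glucose | Named in neither place | Unclear; by default the narrow window |

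**5. Classification in SAP Table 2.** For fat mass this subject is not a completer (did not reach Week 24 on drug), not a retrieved dropout (did not remain in the study), not a non-retrieved dropout (has a value) and not on drug with a missing endpoint. SAP 7.1 nevertheless plans to report these four classes for each key secondary endpoint.

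**6. Upper limit.** Tables 6 to 8 close Week 24 by reference to the first open-label dose. A subject who stopped drug before Week 24 has no such date, so the window has no defined end. This includes the retrieved dropouts, whose data feed the imputation.

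**7. How different an early value could be.** Day 84 is 84/168 = 50% of the period. It is (84 − 28)/7 = 8 weeks after the first glucocorticoid step, against (168 − 28)/7 = 20 weeks at target, or 40%. Day 154 is 92% of the period and 18/20 = 90% of the time since that step.

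**8. Size, on assumed values.** The documents give no dropout rate. Let p be the share of the crinecerfont arm with such a value, and f the fraction of the full effect it carries.
- Against a placebo-like imputation carrying no effect, the arm mean differs by p × f: 0.02 × 0.4 = 0.8% of the full effect at the low end, 0.05 × 0.4 = 2% to 0.05 × 0.9 = 4.5% in the middle, and 0.10 × 0.9 = 9% at the high end. In an arm of 110, these shares are about 2 to 11 subjects.
- Against a true 24-week on-drug value, the difference is p × (1 − f), from 0.02 × 0.1 = 0.2% to 0.10 × 0.6 = 6%, in the opposite direction.

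The same rule also acts in the placebo arm, and the values of any retrieved dropouts are unknown. The net sign cannot be fixed.

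**9. Checking a Day 155 opening.** The Week 24 visit is ±5 days, and the DXA may precede it by up to 7 days (Protocol 9.3.8). The earliest on-schedule scan is 168 − 5 − 7 = Day 156, inside the window. A repeat scan is allowed within 2 weeks of the visit, so the latest is 168 + 5 + 14 = Day 187. That is beyond Day 182 but within 182 + 14 = Day 196.

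**The case against.** The strongest counter-argument is Table 5. Its title covers subjects who stop study drug before Week 24, and SAP 6.7 does not limit it by assessment where it introduces it. On that reading the Day 90 DXA maps to Week 12 and Week 24 is imputed, as it should be. This reading is possible but weaker: the same paragraph sends DXA and the other infrequent tests to Tables 6 to 8 without exception. At best, the SAP contains two rules for the same scan.

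The defence can also say that SAP 6.7 gives infrequent assessment as the reason for all the broader windows, and that the midpoint rule is prespecified. That explains why no other visit competes for the interval. It does not show that a Day 85 scan represents Week 24. The SAP itself is stricter with body composition than with bone density: 2 weeks against 1 month for a late baseline (SAP 6.3.1), and 14 against 28 days after the open-label dose.

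Exposure is limited, and this stands. Subjects who stop drug are meant to stay in the study (Protocol 9.10), and a later scan nearer Day 168 would take precedence.

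A reader might also infer more than the text supports:
- **That HOMA-IR is certainly affected.** It needs glucose as well as insulin, and fasting glucose is never named as a wide-window test. Read literally, Week 24 glucose would be missing and HOMA-IR imputed.
- **That the glucose tolerance test is part of the problem.** It is not listed at early termination, and its p-value is nominal.
- **That a Day 84 value reflects at most two weeks on the final glucocorticoid dose.** Protocol 9.3.1 allows fewer than four steps, so the last step may come as early as Week 4, leaving 8 weeks. What does hold is that none of the Week 12 to 24 optimization period has elapsed at Day 84.

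**Conclusion.** The point holds for percent total fat mass. On the more natural reading of SAP 6.7 and Table 7, an exit DXA from about Day 84 to Day 154 becomes the observed Week 24 value. It displaces the specified imputation, is handled differently from weight at the same visit, and leaves the subject outside every class in SAP Table 2. For HOMA-IR the finding is only that the window is ambiguous. The missing upper limit for subjects without an open-label dose is a separate gap and follows directly from the tables.

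The effect is probably small. The range of 0.8% to 9% of the full effect rests entirely on assumed withdrawal shares and effect fractions and on a placebo-like comparator, so it illustrates scale and is not an estimate. A reader might infer a bias in favour of crinecerfont, or a dilution of its effect. The documents support neither: shorter exposure reduces the effect, whereas an on-drug value in place of a placebo-based one increases it. The primary endpoint does not use these windows. This is a cheap improvement worth making and does not threaten the trial's main conclusion.

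**What to change.** Amend SAP 6.7 before the Week 24 database lock:

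- **Table 7, Week 24:** set the lower limit to Day 155 and keep the upper limit at first open-label dose + 14 days. For subjects with no open-label dose, use 155 to 196, which is the Table 5 limit of Day 182 plus the 14 days allowed to others. This keeps permitted repeat scans up to Day 187.
- **HOMA-IR:** state that fasting glucose and insulin share one Week 24 window, from Day 155 to the first open-label dose, or 155 to 182 without one.
- **Early values:** summarize body-composition and HOMA-IR values from Day 84 to 154 as early-termination data. If there is nothing later, treat Week 24 as missing and impute under SAP 16.2. A withdrawn subject then falls into the non-retrieved class of SAP Table 2.
- **Precedence:** say that these limits, and not the present Table 7 and 8 bounds, govern subjects who discontinue.
- **Remaining tests:** Table 6 and the other tests in Table 8 can keep their lower limits but need a stated upper limit for subjects without an open-label dose.

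The cost is table wording, a few more imputed values and slightly wider intervals. A subject still on drug whose only scan was done before Day 155 would also be imputed, from the same treatment group.
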